9.1. Statistical Hypotheses

This is an exploratory study with a primary objective of assessing safety and tolerability. Any hypothesis tests conducted for treatment comparisons will be exploratory in nature and conducted without adjustment for multiplicity.

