9.4.3. Secondary Endpoints (PK)

Pharmacokinetic parameter estimates for LY3832479 will be calculated using standard noncompartmental methods of analysis and summarized by dose using descriptive statistics, if sufficient data are available.

The parameters for analysis will be Cmax and AUC of LY3832479. Other noncompartmental parameters, such as time to Cmax, apparent terminal elimination half-life, clearance, and volume of distribution may be reported. Analyses of other PK parameters may be performed, if appropriate.

A compartmental analysis may also be performed to further characterize LY3832479 PK and support model-based PK simulations.

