6. TREATMENTS

The following is a list of the study treatment abbreviations that will be used in the TFLs.

Cohort	Study Treatment Name	Treatment order in TFL
All	Pooled placebo IV	1
1	700 mg LY3832479 IV	2
2	2800 mg LY3832479 IV	3
3	7000 mg LY3832479 IV	4

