9.3.2 Pharmacokinetic statistical methodology

All PK parameters will be summarized by treatment using descriptive statistics.

The PK parameter estimates will be evaluated to delineate dose proportionality. Log-transformed C_{max} , and $AUC(0-\infty)$ of LY3832479 will be evaluated using a power model (where log-dose acts as an explanatory variable) to estimate ratios of dose-normalized geometric means and corresponding 90% confidence intervals. In addition, results of the dose proportionality will be plotted.

The estimated ratio of dose-normalized geometric means of PK parameters between the highest and lowest doses will be used to assess dose proportionality.

Example SAS code for the analysis:

```
proc mixed data=pk;
  model log_pk = log_dose / alpha=0.1 cl solution residual ddfm=kr;
  estimate '700 mg' intercept 1 log_dose 2.87506126 / alpha=0.1 cl; /*Log of 700 */
  estimate '2800 mg' intercept 1 log_dose 3.44715803 / alpha=0.1 cl; /*Log of 2800 */
  estimate '7000 mg' intercept 1 log_dose 3.84509804 / alpha=0.1 cl; /*Log of 7000 */
  estimate '2800 mg - 250 mg' log_dose 0.97003679 / alpha=0.1 cl; /*Difference in
  log values of 7000 and 700 */
  ods output solutionf=est;
  ods output estimates=estims;
run;
```

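### The example SAS code in SAP 9.3.2 uses log10(750) for the 700 mg estimate and a wrong coefficient and label for the 7000 versus 700 mg contrast

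*SAP*

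**What the plan says.** SAP 9.3.2 regresses log-transformed Cmax and AUC(0-∞) on log dose, with 90% confidence intervals. It then names the quantity to be interpreted: "The estimated ratio of dose-normalized geometric means of PK parameters between the highest and lowest doses will be used to assess dose proportionality".

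Under the words "Example SAS code for the analysis" it gives a PROC MIXED step with four ESTIMATE statements: one predicted value for each dose and one contrast. The first is "estimate '700 mg' intercept 1 log_dose 2.87506126 / alpha=0.1 cl; /*Log of 700". The contrast is "estimate '2800 mg - 250 mg' log_dose 0.97003679 / alpha=0.1 cl; /*Difference in", and its comment continues on the next line with "log values of 7000 and 700".

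The doses are 700, 2800 and 7000 mg (SAP Section 6, where the lowest is listed as "700 mg LY3832479 IV"; Protocol 6.1). Neither 250 mg nor 750 mg is among them.

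**The concern.** Two of the four constants do not match the doses that their own comments name. On the contrast line, the label, the comment and the coefficient describe three different dose pairs: 2800 and 250 mg, 7000 and 700 mg, and 7000 and 750 mg.

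This matters because the contrast line is the only place where the highest-to-lowest ratio is specified numerically, and the code exports its result through `ods output estimates=estims`. SAS executes the coefficient and ignores the comment. If the block is carried into the production program, the proportionality ratio spans a 9.33-fold dose range instead of 10-fold and appears under a label naming two other doses. The geometric mean reported for 700 mg is the one predicted at 750 mg. A shift of about 7% would not look implausible in the output, so it could pass unnoticed.

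**Working it through.** **Inputs.** The constants 2.87506126, 3.44715803, 3.84509804 and 0.97003679 come from the code in SAP 9.3.2. The doses 700, 2800 and 7000 mg come from SAP Section 6.

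**Step 1: the log base, from the constants that are right.**
- log10(2800) = 3.44715803, which matches.
- log10(7000) = 3.84509804, which matches.

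The constants are therefore base 10. Natural logs do not fit (ln 700 = 6.551, ln 10 = 2.303).

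**Step 2: the two that do not match.**

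| Line | Constant in code | Back-transformed | Correct value |
|---|---|---|---|
| 700 mg estimate | 2.87506126 | 10^2.87506126 = 750.0 | log10(700) = 2.84509804 |
| Highest vs lowest | 0.97003679 | 10^0.97003679 = 9.333 = 7000/750 | log10(7000/700) = 1.00000000 |

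The two errors agree with each other: 3.84509804 − 2.87506126 = 0.97003678, the stated contrast to within last-digit rounding. A fault in reading the PDF is therefore not a plausible cause. The label does not explain the coefficient either, since log10(2800/250) = 1.04921802.

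**Step 3: effect on the 700 mg geometric mean.** With slope b the prediction is too high by the factor (750/700)^b = 10^(0.02996322·b).
- b = 1: 1.071, or +7.1%.
- b = 0.9: 1.064, or +6.4%.

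**Step 4: effect on the dose-normalized ratio.** The SAP does not show how the contrast is normalized, so both possibilities are worked.
- Correct: 10^(b − 1).
- Wrong constant, normalized by the same 9.33-fold range: 10^(0.97003679·(b − 1)).
- Wrong constant, divided by the true 10-fold dose ratio: 10^(0.97003679·b − 1).

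For the intervals I assume a between-subject CV of 25% (the documents give none), with 7, 7 and 6 participants on active drug as planned.
- SD on the log10 scale: √ln(1 + 0.25²)/ln 10 = 0.10693.
- Sum of squares of log10 dose about its mean: 3.3206.
- SE(slope) = 0.10693/√3.3206 = 0.05868.
- With 18 df, t(0.95) = 1.734, so the half-width for the slope is 0.10176.

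| | Ratio at b = 1 (90% CI) | Ratio at b = 0.9 |
|---|---|---|
| Correct | 1.000 (0.791–1.264) | 0.794 |
| Same wrong constant throughout | 1.000 (0.797–1.255) | 0.800 |
| Wrong constant, divided by 10 | 0.933 (0.744–1.172) | 0.747 |

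Changing the CV (15% to 40% was considered) alters the interval widths but not the point ratios.

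**Step 5: the log base in use.** The SAP does not state the base, and the SAS LOG() function is the natural log. With natural-log data all four constants would be wrong; for instance, exp(0.97003679) = 2.64, so the contrast would span a 2.64-fold range.

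**The case against.** The block is offered as an example. The prose and the comments give the right intent, and a careful programmer or quality-control reader could see the contradiction within single lines. The production program is not among the documents, so any harm is conditional on reuse. All of that is true.

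The effect is also small. If the same wrong constant is used to normalize, exact proportionality still gives 1.000. The 6.7% shortfall arises only when the wrong coefficient is combined with the right divisor, and it lies well inside the assumed 90% interval. No decision depends on the result: the protocol states "This is an exploratory study with a primary objective of assessing safety and tolerability", it plans PK parameters to be "summarized by dose using descriptive statistics, if sufficient data are available", and safety data guide escalation. These points limit the severity. They do not make the constants right, and the protocol contains no other proportionality method to fall back on.

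A further point is that Protocol 6.6 allows later cohort doses to be adjusted without an amendment, so the 2800 and 7000 mg constants could themselves need replacing. That is a fair caution about hard-coded values. It does not excuse the constant for 700 mg, the starting dose, and the code should at least match the doses that the SAP lists. Leaving the normalization to later processing is not an error in itself, but the size of the bias cannot be settled without it.

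**Conclusion.** The concern holds: the code is wrong as written and should be fixed. Two coefficients and one label are in error; the 2800 and 7000 mg constants are correct. If the constants are reused on log10 data, the 700 mg geometric mean is overstated by 7.1% at slope 1 (6.4% at slope 0.9). The highest-to-lowest ratio then compares 7000 mg with 750 mg. Under exact proportionality it is reported as 1.000 or 0.933, according to the unstated normalization. The confidence limits rest on the assumed 25% CV and full planned enrolment; the point figures do not. The fitted slope and its 90% interval, the 2800 and 7000 mg estimates and the descriptive PK summaries are unaffected. With no acceptance limits in an exploratory study, the consequence is a mislabelled and possibly biased secondary PK result, and no pass/fail conclusion changes.

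**What to change.** In SAP 9.3.2:
- replace 2.87506126 with 2.84509804;
- replace 0.97003679 with 1.00000000;
- relabel the contrast line as 7000 mg − 700 mg;
- state that `log_pk` and `log_dose` are both log10, and that the dose-normalized ratio and its 90% limits are 10^(estimate − 1) and 10^(limit − 1).

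Confirm that the production program does not contain the old constants. If a cohort's dose is changed under Protocol 6.6, the affected constants, the label and, where the highest dose changes, the subtracted 1 must be re-derived from the doses actually given.

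The cost is two coefficients, one label and one sentence in the SAP, plus a program check. No new data or participants are needed.

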9.4 Safety and Tolerability Assessments

9.4.1 Adverse events

Where changes in severity are recorded in the Case Report Form (CRF), each separate severity of the AE will be reported in the listings, only the most severe will be used in the summary tables. A pre-existing condition is defined as an AE that starts before the subject has provided written informed consent and is ongoing at consent. A non-treatment emergent AE is defined as an AE which starts after informed consent but prior to dosing. A treatment-emergent AE is defined as an AE which occurs postdose or which is present prior to dosing and becomes more severe postdose.

All AEs will be listed. Treatment-emergent AEs will be summarized by treatment, severity and relationship to the study drug. The frequency (the number of AEs, the number of subjects experiencing an AE and the percentage of subjects experiencing an AE) of treatment-emergent AEs will be summarized by treatment, Medical Dictionary for Regulatory Activities (MedDRA) version 23.0 system organ class and preferred term. The summary and frequency AE tables will be presented for all causalities and those considered related to the study drug by the investigator. Any serious AEs will be listed. Onset times will be calculated from the start of the infusion.

Discontinuations due to AEs will be listed.

9.4.2 Concomitant medication

Concomitant medication will be coded using the WHO drug dictionary (Version WHODD MAR20B3). Concomitant medication will be listed.

9.4.3 Clinical laboratory parameters

All clinical chemistry and hematology data will be summarized by parameter and treatment together with changes from baseline, and listed. Baseline is defined as the Day 1 predose assessment. Additionally, clinical chemistry and hematology data outside the reference ranges will be listed and flagged on individual subject data listings.

9.4.4 Vital signs

Vital signs data will be summarized by treatment together with changes from baseline, where baseline is defined as the Day 1 predose assessment. Figures of mean vital signs and mean changes from baseline profiles will be presented by treatment.

Values for individual subjects will be listed.

9.4.5 Electrocardiogram

All ECGs will be performed for safety monitoring purposes only and will not be presented. Any clinically significant findings from ECGs will be reported as an AE.

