9.4. Statistical Analyses

Statistical analysis of this study will be the responsibility of sponsor or its designee.

All tests of treatment effects will be conducted at a 2-sided alpha level of 0.05, unless otherwise stated, and all confidence intervals will be given at a 2-sided 95% level.

Any change to the data analysis methods described in the protocol will require an amendment only if it changes a principal feature of the protocol. Any other change to the data analysis methods described in the protocol, and the justification for making the change, will be described in the statistical analysis plan (SAP) and the clinical study report. Additional exploratory analyses of the data will be conducted as deemed appropriate.

The SAP will be finalized prior to unblinding and it will include a more technical and detailed description of the statistical analyses described in this section. This section is a summary of the planned statistical analyses of the most important endpoints including primary and key secondary endpoints.

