9.4.2. Primary Endpoints (Safety)

All analyses of primary endpoints will be made on the Safety Population.

All investigational product- and protocol procedure-related AEs will be listed and, if the frequency of events allows, safety data will be summarized using descriptive methodology. The incidence of symptoms for each treatment will be presented by severity and by association with investigational product as perceived by the investigator.

A TEAE is defined as an event that emerges after treatment (ie, after administration of placebo or LY3832479), having been absent pretreatment, or worsens relative to the pretreatment state.

The number of participants who experience a TEAE and/or an SAE (all causalities and related to study drug) will be summarized by study treatment. All TEAEs will be summarized by system organ class and by decreasing frequency within system organ class.

Other safety parameters that will be assessed include safety laboratory parameters, vital signs, and ECG parameters. The parameters will be listed and summarized using summary statistics. Additional analysis will be performed if warranted upon review of the data.

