3. INTRODUCTION

This SAP has been developed after review of the Clinical Study Protocol (final version dated 03 June 2020) and Protocol Amendment (c) (final version dated 15 July 2020).

This SAP describes the planned analysis of the safety, tolerability, and pharmacokinetic (PK) data from this study. A detailed description of the planned TFLs to be presented in the clinical study report (CSR) is provided in the accompanying TFL shell document.

The intent of this document is to provide guidance for the statistical and PK analyses of data. In general, the analyses are based on information from the protocol, unless they have been modified by agreement with Eli Lilly and Company. A limited amount of information concerning this study (e.g., objectives, study design) is given to help the reader's interpretation. When the SAP and TFL shells are agreed upon and finalized, they will serve as the template for this study's CSR.

This SAP supersedes the statistical considerations identified in the protocol; where considerations are substantially different, they will be so identified. If additional analyses are required to supplement the planned analyses described in this SAP, they may be performed and will be identified in the CSR. Any substantial deviations from this SAP will be agreed upon with Eli Lilly and Company and identified in the CSR. Any minor deviations from the TFLs may not be documented in the CSR.

This SAP is written with consideration of the recommendations outlined in the International Conference on Harmonisation (ICH) E9 Guideline entitled Guidance for Industry: Statistical Principles for Clinical Trials¹ and the ICH E3 Guideline entitled Guidance for Industry: Structure and Content of Clinical Study Reports².

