4. STUDY OBJECTIVES

4.1 Primary Objective

To investigate the safety and tolerability of a single dose of LY3832479 in healthy participants.

The primary endpoints are serious and non-serious adverse events (AE), laboratory measures of safety, electrocardiogram (ECG), and vital signs.

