9. STATISTICAL METHODOLOGY

9.1 General

Data listings will be provided for all data that are databased. Summary statistics and statistical analysis will only be presented for data where detailed in this SAP. For continuous data, summary statistics will include the arithmetic mean, arithmetic standard deviation (SD), median, minimum, maximum, and N; for log-normal data (e.g. the PK parameters: AUCs and C_{max}) the geometric mean and geometric coefficient of variation (CV%) will also be presented. For categorical data, frequency count and percentages will be presented. Data listings will be provided for all subjects up to the point of withdrawal, with any subjects excluded from the relevant population highlighted. Summary statistics and statistical analyses will generally only be performed for subjects included in the relevant analysis population. For the calculation of summary statistics and statistical analysis, unrounded data will be used.

Mean change from baseline is the mean of all individual subjects' change from baseline values. Each individual change from baseline will be calculated by subtracting the individual subject's baseline value from the value at the timepoint. The individual subject's change from baseline values will be used to calculate the mean change from baseline using a SAS procedure such as Proc Univariate.

Data analysis will be performed using SAS® Version 9.4 or greater.

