9.4.10 Other assessments

All other safety assessments not detailed in this section will be listed but not summarized or statistically analyzed.

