11. CHANGES FROM THE PROTOCOL SPECIFIED STATISTICAL ANALYSES

There were no changes from the protocol specified statistical analyses.

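### ECG is a primary safety endpoint that the protocol plans to list and summarize, but SAP 9.4.5 presents no ECG data and SAP 11 declares no change

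*SAP*

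**What the plan says.** The objectives table in protocol section 3 includes ECG among the primary safety endpoints. SAP 4.1 repeats this: "The primary endpoints are serious and non-serious adverse events (AE), laboratory measures of safety, electrocardiogram (ECG), and vital signs".

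Protocol 9.4.2, which covers the analysis of the primary endpoints, names the measures to be assessed besides adverse events as safety laboratory parameters, "vital signs, and ECG parameters. The parameters will be listed and summarized using summary statistics". No condition is attached.

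SAP 9.4.3 and 9.4.4 carry this out for laboratory data and vital signs, with summaries by treatment and change from baseline. For ECG, SAP 9.4.5 says: "All ECGs will be performed for safety monitoring purposes only and will not be presented". Clinically significant findings go to adverse event reporting.

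Four other statements bear on the point:

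- SAP 9.1: "Data listings will be provided for all data that are databased".
- SAP 3, in the sentence giving the SAP precedence over the protocol's statistical section: "where considerations are substantially different, they will be so identified".
- Protocol 9.4, on changes that do not touch a principal feature: the change, "and the justification for making the change, will be described in the statistical analysis plan (SAP) and the clinical study report".
- SAP 11: "There were no changes from the protocol specified statistical analyses".

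**The concern.** The SAP keeps ECG as a primary endpoint in section 4.1 and removes its analysis in section 9.4.5, then certifies that it follows the protocol. Followed as written, it produces no ECG intervals, no change from baseline and no comparison with pooled placebo. Rate is partly covered, because pulse rate is summarized with the vital signs; the other ECG parameters are not covered at all.

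A shift that no reader calls clinically significant would then appear nowhere in the study report. The report could say whether clinically significant ECG findings occurred on each treatment, but could not describe the parameters the protocol promised. SAP 3 makes the SAP and its shells the template for the report, so both the gap and the statement of conformity would carry into it.

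**Working it through.** The main check is a comparison of text. No sample size, power or error rate depends on it.

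**Side by side**

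| Question | Protocol | SAP |
|---|---|---|
| Is ECG a primary endpoint? | Yes (section 3) | Yes (4.1) |
| Are ECG parameters listed? | Yes (9.4.2) | No (9.4.5); yes if databased (9.1) |
| Are ECG parameters summarized? | Yes (9.4.2) | No (9.4.5) |
| Must a change be identified? | Yes, with a justification (9.4) | Yes, if substantial (3) |
| Is a change declared? | – | No; section 11 says there was none |

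**Does another SAP section restore the listing?** SAP 9.4.10 reads: "All other safety assessments not detailed in this section will be listed but not summarized or statistically analyzed". ECG has its own subsection, so this catch-all does not reach it.

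**Is the conflict with SAP 9.1 certain?** No. It depends on whether ECG values enter the database. Protocol 10.1.5 says that all participant data are recorded on the CRF or transferred electronically, which implies that they do. Protocol 8.2.2 mentions paper copies held at the site, and no ECG page is described. If the values are not databased, the conflict with 9.1 disappears; the conflicts with protocol 9.4.2, protocol 9.4 and SAP 11 remain. Even if they are databased, the 9.1 conflict concerns listings only, because 9.1 limits summaries to data the SAP details.

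**How much data is involved?** The Schedule of Activities shows post-dose ECGs at 1, 6, 24 and 48 hours and at about 4 outpatient visits, so about 8 per participant. The extracted table may be misaligned, so the count is approximate. Planned participants: 9 + 9 + 8 = 26; maximum 30.

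- Post-dose only: 8 × 26 = 208; 8 × 30 = 240.
- With the Day 1 predose ECG: 9 × 26 = 234; 9 × 30 = 270.
- With the screening ECG as well: 10 × 26 = 260; 10 × 30 = 300.

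**What could a summary show?** The documents give no ECG variability, so the standard deviation (SD) of change in an interval is assumed to be 8 to 20 ms. Pooled placebo is 2 + 2 + 2 = 6. For one dose group of size n at one time point, the 95% half-width for the difference in mean change is

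t(0.975, n + 4) × SD × √(1/n + 1/6).

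| n | t | SD 8 ms | SD 10 ms | SD 15 ms | SD 20 ms |
|---|---|---|---|---|---|
| 7 | 2.201 | 9.8 | 12.2 | 18.4 | 24.5 |
| 6 | 2.228 | 10.3 | 12.9 | 19.3 | 25.7 |

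For example, with n = 7 and SD 10 ms: 2.201 × 10 × √(0.1429 + 0.1667) = 12.2 ms. The half-width is a gauge of precision only; SAP 9.4.11 plans no inferential safety analysis.

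**The case against.** The strongest defence is that this is a disclosure slip. SAP 3 says the SAP supersedes the protocol's statistical section, so it is clear which text governs, and 9.4.5 states its approach openly with a short reason. ECG is reduced to an event-level outcome and not dropped: protocol 8.2.2 already sends clinically significant findings that lead to a diagnosis to adverse event reporting, and treatment-emergent events are tabulated by treatment. Each tracing is read on site, and safety data are reviewed before escalation, so participant monitoring is unaffected. The study is unpowered, no safety inference is planned, and a summary would be imprecise.

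Much of this is right about consequences. No dose decision, error rate or sample size depends on the point, and the gap is in reporting, not in monitoring. The half-widths also rest on assumed standard deviations.

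It does not remove the conflict. The sentence that gives the SAP precedence also requires substantial differences to be identified, and SAP 11 denies that there are any. Safety monitoring as a reason does not separate ECG from laboratory data and vital signs, which are also safety measures and are summarized. Adverse events are already a primary endpoint component in their own right, so reporting ECG only through them leaves ECG with no output of its own. Nor does a later protocol change explain the difference: the SAP was written against Protocol Amendment (c), the visible part of the change log lists only swab-related edits, and the current protocol 9.4.2 keeps the ECG commitment.

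**Conclusion.** The concern holds. One of the four primary endpoint components loses the listing and summary that protocol 9.4.2 promises, and the statement in SAP 11 is incorrect. This rests on explicit text and needs no assumption.

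The further conflict with SAP 9.1 holds only if ECG values are databased, which the documents suggest but do not settle. The practical loss is descriptive: about 208 to 240 post-dose ECGs would yield no parameter-level result, in a study where such a result would reveal only fairly large shifts (half-width about 10 to 26 ms under the assumed standard deviations). The correction is needed whichever route is chosen, because the two documents cannot both be followed.

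**What to change.** **Preferred.** Replace SAP 9.4.5 with text to this effect: *ECG parameters entered in the CRF will be listed for each participant and summarized by treatment, including pooled placebo, and by time point, with change from the Day 1 predose value; clinically significant findings will in addition be reported as adverse events.* This follows SAP 9.4.4, meets protocol 9.4.2, removes any conflict with SAP 9.1 and makes SAP 11 correct on this point. The cost is one paragraph and probably two or three table and listing shells; the shell document was not available to check. If the values are not in the database, they would have to be transcribed from the stored tracings: about 234 to 270 including predose, or 260 to 300 with screening as well.

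**If the values are not databased and will not be entered.** Record the departure and its justification in SAP 11 and the study report, state in both that ECG is assessed only through adverse events, and reconcile the primary endpoint wording in SAP 4.1 and the protocol. This costs one entry and matching report text, at the price of no ECG parameter data for a primary endpoint component. Removing ECG from the protocol's endpoints may change a principal feature and so require an amendment under protocol 9.4.

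Neither route alters the design or the maximum of 30 participants.
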